12	CHANGES IN THE PLANNED ANALYSIS	25
13	REFERENCES.....	27
14	APPENDICES.....	28
14.1	SCHEDULE OF STUDY PROCEDURES	28

List of Abbreviations

AE	adverse event
ALC	absolute lymphocyte count
ANC	absolute neutrophil count
ATC	Anatomical Therapeutic Chemical
AUC	area under the curve
BLQ	below the limit of quantitation
BMI	body mass index
BUN	blood urea nitrogen
CBIA	cell-based infectivity assay
CMH	Cochran Mantel-Haenszel
CI	confidence interval
CNI	calcineurin inhibitor
CTMS	Clinical Trial Management System
CYP	cytochrome P450
DMC	Data Monitoring Committee
EAC	Endpoint Adjudication Committee
ECG	electrocardiogram
eCOA	electronic clinical outcome assessment
eCRF	electronic case report form
eGFR	estimated Glomerular Filtration Rate
EOS	End-of-Study
EOT	End-of-Treatment
<hr/>	
FSH	follicle-stimulating hormone
HCT	hematopoietic cell transplant
HDPE	high-density polyethylene
ICF	informed consent form
ICH	International Council for Harmonisation of Technical Requirements for Pharmaceuticals for Human Use
ICU	intensive care unit
IRT	interactive response technology
ITT	intent-to-treat
IWRS	Interactive Web Response System
LLOQ	lower limit of quantitation
LOD	lower limit of detection
LRTC	lower respiratory tract complication
LRTI	lower respiratory tract infection
MAARI	medically attended acute respiratory infection
MDRD	Modification of Diet in Renal Disease
MedDRA	Medical Dictionary for Regulatory Activities
mITT	modified intent-to-treat
mTOR	mammalian target of rapamycin
NCI-CTCAE	National Cancer Institute Common Terminology Criteria for Adverse Events
NRR	Not reportable result

PK	pharmacokinetic(s)
PP	per protocol
PT	preferred term
QD	once daily
QTcF	QT interval corrected for heart rate according to Fridericia
RAV	resistance-associated variant
RBC	red blood cell count
RSV	respiratory syncytial virus
RT-qPCR	quantitative reverse transcription polymerase chain reaction
SAE	serious adverse event
SAF	safety
SAP	statistical analysis plan
SD	standard deviation
SE	standard error
SOC	system organ class
TEAE	treatment-emergent adverse event
TD	Target detected
TND	Target not detected
TSS	total symptom score
ULN	upper limit of normal
URTI	upper respiratory tract infection
WBC	white blood cell count
WHO	World Health Organization

1 Introduction

Respiratory syncytial virus is the leading cause of lower respiratory tract infection (LRTI) and presents a significant health challenge in infants, small children, elderly, and immunocompromised patients, such as those who have received HCT (*Falsey et al., 2005; Hall et al., 2009; Shook and Lin, 2017; Khawaja and Chemaly, 2019*). Respiratory syncytial virus is one of the most common community acquired respiratory viruses that may lead to death in HCT recipients, second only to influenza (*Khawaja and Chemaly, 2019*). The use of ribavirin has been associated with clinical benefit (e.g., reduced rates of progression from upper to lower respiratory tract infection and decreased mortality) in observational studies and case series. Currently, there is no vaccine or highly effective treatment available for RSV.

To address the unmet medical need for more effective antiviral therapies for RSV and based on the promising early nonclinical safety and pharmacological profile, Enanta Pharmaceuticals, Inc. is investigating EDP-938 in humans as a potential treatment for RSV infection. This Phase 2b study, EDP-938-103, is a randomized, double-blind, placebo-controlled, multicenter study designed to assess the efficacy, safety, and tolerability of EDP-938 compared with placebo in adult hematopoietic cell transplant (HCT) recipients with an acute RSV infection and symptoms of an upper respiratory tract infection (URTI).

This statistical analysis plan (SAP) is based upon the protocol (version 8.0, dated 7 March 2023) for this Phase 2b clinical study, and is prepared in compliance with [International Conference on Harmonisation \(ICH\) E3, E6 and E9](#). Furthermore, this SAP contains definitions for analysis sets, derived variables, and statistical methods and data presentations for the analysis of efficacy and safety endpoints.

The study was terminated on September 12, 2023, due to slow enrollment. The decision was made by the sponsor. This statistical analysis plan describes the analyses that will be conducted based on the data collected up until the study terminated. The changes from the originally planned analyses in the protocol is described in [Section 12](#).

2 Objectives

[figure not shown]
2.1 Primary Objective

- To evaluate the effect of EDP-938 on the development of lower respiratory tract complication (LRTC) in HCT subjects with an acute RSV infection of the upper respiratory tract

2.2 Secondary Objectives

- To evaluate the effect of EDP-938 on RSV viral load as measured by quantitative reverse transcription polymerase chain reaction (RT-qPCR) of nasopharyngeal swab samples
- To evaluate the effect of EDP-938 on progression to respiratory failure or all-cause mortality

- [REDACTED]
- To evaluate the pharmacokinetics (PK) of EDP-938 [REDACTED]
- To evaluate the safety and tolerability of EDP-938

3 Investigational Plan

3.1 Overall Study Design and Plan

[figure not shown]
This is a Phase 2b, randomized, double-blind, placebo-controlled, multicenter study evaluating the efficacy and safety of EDP-938 in HCT recipients with acute RSV infection and symptoms of URTI.

The study has 3 periods:

- Screening Period will occur from Day -1 to Day 1. During this period, subjects will review and sign the ICF. Subjects will undergo screening assessments. Screening should be completed as soon as possible, and the subject will be randomized and administered the first dose of study drug within 24 hours of signing the ICF. A subject will be considered enrolled at the time of randomization.
- Treatment Period will begin with the first dose of study drug on Day 1 and will conclude with the End-of-Treatment (EOT) Visit on Day 21.
- Follow-up Period for safety will begin following the last dose of study drug and will conclude at the End-of-Study (EOS) visit on Day 49, 28 days following the last dose of study drug.

An overview of the study design is shown in [Figure 1](#). Study site visits and assessments are detailed in the Schedule of Study Procedures ([Appendix 14.1](#)).

Figure 1: Study Design

3.2 Study Endpoints

3.2.1 Primary Endpoint

- Incidence of LRTC through Day 28 defined as at least one of the following as determined by the Endpoint Adjudication Committee
 - LRTI by RSV
 - LRTI as secondary bacterial pneumonia
 - LRTI by unusual pathogens
 - LRTC of unknown etiology

3.2.2 Secondary Endpoints

- Change in RSV RNA viral load from Baseline through Day 49 in nasopharyngeal swab samples by RT-qPCR
- Incidence of subjects with RSV RNA viral load below the limit of detection in subjects receiving EDP-938 through Day 49
- Plasma PK concentrations of EDP-938
- Safety endpoints include, but are not limited to, adverse events (AEs), serious adverse events (SAEs), vital sign measurements, pulse oximetry measurements, and clinical laboratory test results (including chemistry, hematology, and urinalysis)

3.3 Treatments

EDP-938 drug product tablets and the corresponding placebo tablets are supplied as 150 mg tablets and 200 mg tablets in [REDACTED]
[REDACTED]

Following randomization on Day 1, subjects will receive the first dose of EDP-938 or placebo orally while at the study site. After the first dose, subjects will be instructed to take the study drug orally once daily (QD) on each of the 20 subsequent days. [REDACTED]
[REDACTED]

- [REDACTED]
- [REDACTED]
- [REDACTED]

Subjects will be instructed to take the study drug at approximately the same time every day (± 1 hour).

[REDACTED]
[REDACTED]
[REDACTED]
[REDACTED]
[REDACTED]
[REDACTED]

4 General Statistical Considerations

All analyses will be conducted using SAS Version 9.4 or higher.

Continuous data will be described using descriptive statistics (i.e. n, mean, standard deviation (SD), median, 25th percentile, 75th percentile, minimum, and maximum). For the summary statistics of all numerical variables unless otherwise specified, minimum and maximum will be displayed to the same level of precision as reported. Mean and median will be displayed to one level of precision greater than the data collected. Standard deviation / standard error (SE) will be displayed to two levels of precision greater than the data collected. If the precision of the values being summarized are too large (e.g. 3 or more decimal places), then limit the precision to two decimal places and follow the rules previously stated above. For derived data, the precision of values will be determined on a case-by-case basis. If n=0, then display n and leave all other statistics blank. If n=1, display “N/A” for SD and SE.

Categorical data will be described using the subject count and percentage in each category. When count data are presented, the percentage will be suppressed when the count is zero. A row denoted “Missing” will be included in count tabulations where specified on the shells to account for dropouts and missing values where applicable. The denominator for all percentages will be the number of subjects in that treatment within the analysis set of interest, unless otherwise specified. Non-zero percentages will be rounded to one decimal place, except 100% will be displayed without any decimal places.

Summary Tables will be presented by treatment group. Tables values for treatment group will be labelled as follows: • “EDP-938” • “Placebo”. Models will include stratification factors, ribavirin treatment (present or absent) and ALC (<200 or \geq 200 cells/ μ L), unless an insufficient amount of data exists where convergence or the analysis cannot be performed.

All subject data, including those derived, will be presented in individual subject data listings. Dates will be shown in subject listings as they have been recorded. Unless otherwise stated, unscheduled visit results will be included in date/time chronological order, within subject listings only. All listings will be sorted by subject number, date/time and visit. The treatment group (randomized) as well as subject’s sex and age will be stated on each listing. Unless otherwise stated, data listings will be based on all subjects randomized.

When no data are available for a table or listing, an empty page with the title will be produced with suitable text (e.g., “There are no records for this table/listing.”). For analyses where convergence or the analysis cannot be performed, “NC” (not calculable) will be presented in summary tables.

Unless otherwise specified, baseline will be defined as the last non-missing measurement collected on or before the date of the first dose of study treatment. For subjects who are randomized, but not treated, the baseline will be defined as the last non-missing measurement on or before the date of randomization. The date of first dose will be collected on the Day 1 Study Drug eCRF and the date of last dose will be the date collected on the End of Treatment eCRF.

For the reporting of this study both CDISC SDTM (SDTM Implementation Guide version 3.2) and ADaM (ADaM Implementation Guide version 1.1) standards will be applied. A subject will be considered to have completed the study after his/her attendance at the last planned study visit (Day 49 ± 2 days), or the last unscheduled visit (if any occur), as applicable. For each subject his or her study completion status (Yes/No) is recorded on the End of Study CRF.

4.1 Sample Size

When the study was terminated, there were 9 subjects randomized.

4.2 Randomization, Stratification, and Blinding

Subjects who had completed screening assessments and were eligible for participation in the study were randomized to blinded treatment before the first dose of study drug (Day 1) in a 2:1 ratio to [REDACTED] EDP-938 or placebo administered orally for 21 days. Subject

randomizations were stratified by ribavirin treatment (present or absent) and ALC (<200 or \geq 200 cells/ μ L) at Screening. Assignments to treatment groups were determined by a computer-generated random sequence using an IWRS. The IWRS was used to assign investigational product to each subject. A unique four-digit randomization identifier was assigned by interactive response technology (IRT), which will become the subject number and be used to identify the subject throughout the study.

The study was double-blinded, meaning subjects, investigators, site staff and the CRO/Sponsor study team were blinded to treatment assignment until the completion of the study. During the study, investigators, site personnel, and blinded CRO/Sponsor study team did not have access to results for individual subjects that could impact clinician assessments, including results for RSV viral load, confirmatory respiratory pathogen panel testing, biomarkers, and PK.

4.3 Analysis Populations

4.3.1 Intent-to-Treat (ITT)

The intent-to-treat (ITT) population will include all subjects who receive at least one dose of study drug. All subjects in the ITT population will be analyzed according to the treatment as randomized. The ITT population will be used for the primary efficacy analysis [REDACTED]

4.3.2 Modified Intent-to-Treat by RT-qPCR (mITT by RT-qPCR)

The modified intent-to-treat by RT-qPCR (mITT by RT-qPCR) population will include all subjects in the ITT population, excluding subjects who have undetectable or missing RSV viral load by RT-qPCR at baseline. The mITT by RT-qPCR population will be used for efficacy analysis on RSV viral load by RT-qPCR. This population will exclude subjects with baseline value reported as TND (target not detected), NOR (No valid result), QNS (Quantity Not Sufficient) or not done.

4.3.3 Modified Intent-to-Treat by CBIA (mITT by CBIA)

The modified intent-to-treat by CBIA (mITT by CBIA) population will include all subjects in the ITT population, excluding subjects who have undetectable or missing RSV viral load by CBIA at baseline. The mITT by CBIA population will be used for efficacy analysis on RSV viral load by CBIA. This population will exclude subjects with baseline value reported as TND (target not detected), NRR (not reportable result) or not done.

4.3.4 Safety (SAF)

The safety (SAF) population will include all subjects who received at least one dose of study drug. All subjects in the safety population will be analyzed according to the treatment actually received.

4.3.5 Pharmacokinetic (PK)

The pharmacokinetic (PK) population will include all subjects receiving active study drug and having any measurable plasma concentration of study drug at any timepoint.

4.4 Data Handling Strategy

4.4.1 Study Days and Visit Windows

Study day is defined as the number of days from the date of first dose. Day 1 is the date of the first dose. For assessments or events that occur after the first dose date, study day is calculated as the date of interest minus first dose date plus 1 day. For assessments or events that occur before the first dose date, study day is calculated as the date of interest minus the first dose date.

Analysis visit windows are described in the tables below. Analysis visits are based on nominal scheduled visits and will be used for by-visit analyses or summaries unless otherwise specified in the respective analysis sections. Unscheduled visits and visits performed for early discontinuation will not be included in the by-visit summary or analyses.

- Unscheduled visits including repeat central laboratory assessments for the EOS visit to follow an AE for resolution will not be included in the by-visit analyses/ summaries, but will be included in the listings and other types of analyses/summaries as applicable (e.g. AUC, time to event and treatment emergent safety abnormalities any time post-baseline). For subjects who discontinues study treatment, they should complete a EOT visit and this visit will be labeled as “Early Disc/EOT”. For these subjects, they should also complete FU1 visit and FU2 visit, and these visits will be labeled as “Early Disc/FU1” and “Early Disc/FU2”.
- For subjects who completes study treatment and discontinues study before Day 28, they should complete FU1 visit and this visit will be labeled as “Early Disc/FU1”. For subjects who discontinues study between Day 28 and Day 49, they should complete FU2 visit and this visit will be labeled as “Early Disc/FU2”.

[figure not shown]
Vital signs and safety laboratory tests:

[figure not shown]
Analysis Visit #	Analysis Visit Label	Target Day	Derivation
1	Day 1	1	Based on nominal visit of V1
4	Day 4	4	Based on nominal visit of V2
7	Day 7	7	Based on nominal visit of V3
11	Day 11	11	Based on nominal visit of V4
16	Day 16	16	Based on nominal visit of V5
21	Day 21	21	Based on nominal visit of V6 if subject completes treatment

28	Day 28	28	Based on nominal visit of FU V1 if subject completes treatment and last visit is FU V2.
97	Early Disc/EOT	NA	Based on nominal visit of V6 if subject discontinues treatment
98	Early Disc/FU1	NA	Based on nominal visit of FU V1 if subject discontinues treatment or last visit is FU V1.

RSV viral load by both RT-qPCR and CRIA:

Analysis Visit #	Analysis Visit Label	Target Day	Derivation
1	Day 1	1	Based on nominal visit of V1
4	Day 4	4	Based on nominal visit of V2
7	Day 7	7	Based on nominal visit of V3
11	Day 11	11	Based on nominal visit of V4
16	Day 16	16	Based on nominal visit of V5
21	Day 21	21	Based on nominal visit of V6 if subject completes treatment
28	Day 28	28	Based on nominal visit of FU V1 if subject completes treatment and last visit is FU V2.
49	Day 49	49	Based on nominal visit of FU V2 if subject completes treatment and study
97	Early Disc/EOT	NA	Based on nominal visit of V6 if subject discontinues treatment
98	Early Disc/FU1	NA	Based on nominal visit of FU V1 if subject discontinues treatment or last visit is FU V1.
99	Early Disc/FU2	NA	Based on nominal visit of FU V2 if subject discontinues treatment or study.

ECG:

Analysis Visit #	Analysis Visit Label	Target Day	Derivation
-1	Screening	-1	Based on nominal visit of Screening
4	Day 4	4	Based on nominal visit of V2
11	Day 11	11	Based on nominal visit of V4
21	Day 21	21	Based on nominal visit of V6 if subject completes treatment.
28	Day 28	28	Based on nominal visit of FU V1 if subject completes treatment and last visit is FU V2.
97	Early Disc/EOT	NA	Based on nominal visit of V6 if subject discontinues treatment
98	Early Disc/FU1	NA	Based on nominal visit of FU V1 if subject discontinues treatment or last visit is FU V1.

PK:

Analysis Visit #	Analysis Visit Label	Target Day	Timepoint* Assessment	Derivation
1	Day 1	1	1	Based on nominal visit of V1
1	Day 1	1	2	Same as above
4	Day 4	4	1	Based on nominal visit of V2
7	Day 7	7	1	Based on nominal visit of V3
7	Day 7	7	2	Same as above
11	Day 11	11	1	Based on nominal visit of V4
16	Day 16	16	1	Based on nominal visit of V5

21	Day 21	21	1	Based on nominal visit of V6 if subject completes treatment
21	Day 21	21	2	Same as above
97	Early Disc/EOT	NA		Based on nominal visit of V6 if subject discontinues treatment

* On Day 1, Day 7, and Day 21, two plasma PK samples will be collected (one predose and one postdose) and thus are assigned as Timepoint 1 and 2. At all other visits, only predose samples will be collected.

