8.2.2 Change from Baseline in RSV viral load by RT-qPCR over time

Observed and change from baseline values for RSV viral load by RT-qPCR will be summarized with descriptive statistics by visit (Days 1, 4, 7, 11, 16, 21, 28, and 49) for each treatment group based on mITT by RT-qPCR population and will include the number of non-missing measurements, mean, standard deviation, median, minimum, 25th percentile, 75th percentile, and maximum.

8.2.3 Proportion of subjects with RSV viral load by RT-qPCR below the LOD over time

The proportion of subjects with RSV viral load by RT-qPCR below the limit of detection (LOD) will be summarized by visit (Days 4, 7, 11, 16, 21, 28, and 49) for each treatment group based on mITT by RT-qPCR population.

[REDACTED]

[REDACTED]

[REDACTED]

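### SAP 4.4.1 counts FU V1 as Day 28 only when the subject's last visit is FU V2, so Day 28 viral load and laboratory summaries depend on later attendance

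*SAP*

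**What the plan says.** SAP 4.4.1 assigns analysis visits from nominal visits. Its tables for vital signs and laboratory tests, for RSV viral load and for ECG share the same Day 28 row: "Based on nominal visit of FU V1 if subject completes treatment and last visit is FU V2". The other FU V1 records go to a row labelled Early Disc/FU1, which has no target day: "Based on nominal visit of FU V1 if subject discontinues treatment or last visit is FU V1". The introduction to the same section says what happens to such records: "Unscheduled visits and visits performed for early discontinuation will not be included in the by-visit summary or analyses".

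The text above the tables sets out when each label is meant to apply. Subjects who stop treatment early have their FU1 and FU2 visits labelled as early-discontinuation visits. For treatment completers, the Early Disc/FU1 label is tied to leaving before Day 28: "For subjects who completes study treatment and discontinues study before Day 28, they should complete FU1 visit". For later leavers the text expects a different visit: "For subjects who discontinues study between Day 28 and Day 49, they should complete FU2 visit".

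Two viral load outputs use the Day 28 label. SAP 8.2.2 states: "Observed and change from baseline values for RSV viral load by RT-qPCR will be summarized with descriptive statistics by visit". SAP 8.2.3 states: "The proportion of subjects with RSV viral load by RT-qPCR below the limit of detection (LOD) will be summarized by visit". Both include Day 28. SAP 9.2 adds by-visit laboratory tables, with Day 28 as the last scheduled test. SAP 8.2.3 names no denominator. The default in SAP Section 4 is: "The denominator for all percentages will be the number of subjects in that treatment within the analysis set of interest, unless otherwise specified".

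**The concern.** Whether a sample counts as a Day 28 sample should be settled on Day 28. Under the table it is settled up to three weeks later, by whether the subject attends FU V2. Subjects who attend Day 28 and never return may differ from those who do, through death or loss to follow-up, so the Day 28 summary describes a group selected on a later event that may be related to outcome.

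The case is plausible here. The protocol set all-cause mortality through Day 49 as a secondary endpoint, and its Section 1.2 cites mortality of 21% to 83% in transplant recipients once RSV has reached the lower tract.

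The affected tables also carry much of what is left after the early termination. SAP Section 12 deletes time to viral load below the limit of detection (LOD), so 8.2.3 is the remaining by-visit view of viral clearance. It also drops the incidence of treatment-emergent laboratory abnormalities, so the by-visit tables are the laboratory summary that 9.2 still specifies. A Day 28 laboratory value is then kept or dropped according to attendance at a Day 49 visit for which SAP 9.2 lists no laboratory test.

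**Working it through.** The plan states no figure on this point, so there is none to reproduce. The check applies the rule to cases and then works through the proportion below the LOD.

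**Step 1. Apply the table and the text to the same subjects** (all attend FU V1).

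| Case | Label from the table | Label from the text |
|---|---|---|
| Completes treatment, attends FU V1 and FU V2 | Day 28 | Day 28 |
| Completes treatment, FU V1 on schedule, then dies or is lost | Early Disc/FU1, excluded | Not given that label |
| Completes treatment, leaves between Day 28 and Day 49, returns for FU V2 | Day 28 | Only the FU2 visit is an early-discontinuation visit |
| Completes treatment, leaves before Day 28, FU V1 is the last visit | Early Disc/FU1, excluded | Early Disc/FU1 |
| Stops treatment early, attends all visits | Early Disc/FU1, excluded | Early Disc/FU1 |

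Only the second row disagrees. The text expects an FU2 visit from such a subject, which cannot happen after death or loss to follow-up. The trigger is not attending FU V2. It is not study withdrawal as such, because the subject in the third row keeps Day 28. Read literally, a completer whose last visit is an unscheduled one after FU V2 meets neither row.

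**Step 2. Which outputs use the label.** Affected: viral load by visit (8.2.2), proportion below the LOD by visit (8.2.3) and laboratory tests by visit (9.2). Not affected: ECG and vital signs, which are only listed (9.5, 9.3); viral load AUC, which uses the available assessments at their actual times (8.2.1); the LRTC summary (8.1.1); and the listings.

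**Step 3. Weight of one subject.** SAP 4.1 gives 9 randomised. The split by arm is not given. At exactly 2:1 it would be 6 and 3. One subject is then 1/6 = 16.7% or 1/3 = 33.3% of an arm. The viral load summaries use the mITT by RT-qPCR population, whose size is not stated. If it is smaller, each subject weighs more.

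**Step 4. Effect on the proportion below the LOD.** The counts are assumed. Every subject in the arm has an FU V1 result, and one of them is relabelled.

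| Arm size | All FU V1 results | Relabelled subject | Full-arm denominator | Observed denominator |
|---|---|---|---|---|
| 3 | 2/3 = 67% | below LOD | 1/3 = 33% | 1/2 = 50% |
| 3 | 2/3 = 67% | detectable | 2/3 = 67% | 2/2 = 100% |
| 6 | 3/6 = 50% | below LOD | 2/6 = 33% | 2/5 = 40% |
| 6 | 3/6 = 50% | detectable | 3/6 = 50% | 3/5 = 60% |

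The reported proportion can fall, rise or stay the same. Where it moves in these examples, the shift is 10 to 33 percentage points.

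**The case against.** The strongest reply is that little rides on this. Withdrawers between Day 28 and Day 49 are asked back for FU V2 and keep their Day 28 record if they come. Only completers with no FU V2 at all are caught, among at most 9 subjects, and the documents do not say that there is even one. No tests are planned, and for so few subjects the listings show every value. All of this is fair and limits the size of the point. It does not make the rule right: the table still contradicts the text, and a programmer cannot follow both.

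A reader might also infer several stronger things that the documents do not support:

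- *That clearance at Day 28 is understated.* Step 4 shows that this needs a dropped subject who was below the LOD. With a detectable subject, the full-arm figure does not change and the observed-denominator figure rises.
- *That the full-arm default amounts to imputation, against SAP Section 8.* SAP Section 4 provides for a row of missing values in count tables where the shells call for one. The shells are not available, so a conflict is not shown.
- *That the sponsor's termination cut off follow-up after Day 28.* SAP Section 1 gives slow enrolment as the reason for stopping and does not say that follow-up was shortened.
- *That visits should be remapped by study day, including those of treatment discontinuers.* The nominal-visit approach is deliberate, and the table and the text agree on discontinuers. A strict window (Day 28 ± 1 day) could drop a late FU V1, for example on Day 30, that the present rule keeps.

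**Conclusion.** The Day 28 rule in SAP 4.4.1 is wrong as written. It makes a valid on-schedule measurement depend on a later event, and it goes beyond the section's own text. The consequence is confined to the by-visit Day 28 summaries of viral load (8.2.2, 8.2.3) and safety laboratory tests (9.2). The ECG table has the same wording, but no ECG summary is produced.

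The labelling conclusion rests on the text alone and needs no assumption. The size does need one: under a 6:3 split, one relabelled subject is 17% or 33% of an arm's Day 28 data. No direction can be claimed without knowing that subject's viral status and the denominator used. Whether any subject is affected cannot be told from the documents.

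**What to change.** Keep nominal visits and change the wording in three places.

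1. In the Day 28 rows for vital signs and laboratory tests, viral load and ECG, delete the condition that the last visit is FU V2. FU V1 then counts as Day 28 for any treatment completer to whom the revised Early Disc/FU1 row does not apply, whatever happens afterwards. State this exception so that the two rows cannot overlap.
2. Change the Early Disc/FU1 rows to cover subjects who discontinue treatment, or who complete treatment and discontinue the study before Day 28. This matches the text, and it also settles the case of an unscheduled last visit.
3. In SAP 8.2.3, report the number with a Day 28 result and the number missing alongside the proportion below the LOD, so that the denominator is visible.

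The cost is SAP wording and a small change in visit mapping, with no new data. Protocol 11.1 bars SAP changes after unblinding. If that point has passed, describe the issue in the clinical study report and show the Day 28 summaries under both labels.
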